## 8.2.3. Electrocardiograms

- At each timepoint indicated in the SoA (Section 1.3), 12-lead ECGs will be performed in triplicate sequentially within 5 minutes, at least 1 minute apart to obtain heart rate, PR, QRS, QT, and QTc intervals.
- ECGs should not be performed within 1 hour after any major meal or major meals should be withheld until after ECG assessments.
- Participants should rest in supine position for at least 10 minutes before each ECG timepoint.
- Predose ECGs (Baseline) should be performed at least 1 minute apart after 10 minutes of bedrest in supine position (note, no bedrest is required post ECG), at 90, 75, and 60 minutes before dosing.
- Postdose ECGs will be performed before the coinciding blood collection, whenever possible.

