## 8.3.1. Time Period and Frequency for Collecting AE and SAE Information

- All AEs and SAEs will be collected from the signing of the ICF until the EOS visit on Day 75 as specified in the SoA (Section 1.3).
- All SAEs will be recorded and reported to Alexion immediately and under no circumstance should this exceed 24 hours of the Investigator's awareness, as indicated in Section 10.3. The Investigator will submit any updated SAE data to Alexion within 24 hours of the date the investigational site became aware of the event.
- Investigators are not obligated to actively seek AE or SAE data after conclusion of the study participation. However, if the Investigator learns of any SAE, including a death, at any time after a participant has been discharged from the study, and they

consider the event to be reasonably related to the study intervention or study participation, the Investigator must promptly notify Alexion.

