2.1 Primary Objective

Objective	Endpoint
• To assess the safety and tolerability of ALXN1910	• Incidence of TEAEs and TESAEs

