4.13.1 Adverse Events

All outputs for AEs/treatment-emergent adverse events (TEAEs) will be based on the SAF unless specified separately in TLF shells. AEs will be coded using the Medical Dictionary for Regulatory Activities (MedDRA®), version 24.1 or latest.

All AE summaries should provide the number and percentages of participants reporting at least one AE and the total number of events reported.

Summaries of AEs will include the following:

- Incidence of TEAEs (by dose and by cohort and overall, SOC, and PT)
- Incidence of TEAEs by highest relationship (by cohort and overall, SOC, and PT)
- Incidence of TEAEs by worst severity (mild/moderate/severe/life threatening/fatal, by cohort and overall, SOC, and PT)

Summary tables will contain counts of participants, percentages of participants in parentheses, and the number of events where applicable. A participant who has multiple events in the same SOC and PT will be counted only once in the participant counts, but all events will be included.

All Adverse Events (AEs)

All AEs will be listed including pretreatment AEs.

Treatment-emergent Adverse Event (TEAE)

A TEAE will be defined as any AE that emerges during treatment (i.e., an AE that started after study drug administration or pre-existed that worsened in severity after study drug administration) and will be analyzed for the purpose of safety analysis.

TEAEs will be summarized by SOC and PT, including the number and percentage of participants experiencing events, separately.

A by-participant listing of all TEAEs leading to withdrawal from the study will be provided.

Severity

TEAEs will be summarized by SOC, PT, and severity, including the number and percentage of participants experiencing events. If a participant reports the same TEAE more than once within that SOC and PT, the TEAE with the highest severity will be used in the corresponding severity summaries.

In summaries including severity, the following intensity categories will be summarized as per CTCAE version 5.0 published 27 Nov 2017: 'Mild', 'Moderate', 'Severe', 'Life-threatening', 'Fatal'. Participants who experience the same event multiple times will be included in the most severe category. Events with missing intensity will be considered as 'Severe' events for summary purposes but recorded as missing in the listings.

If severity is reported by Common Terminology Criteria for Adverse Events (CTCAE) grade, then summary of severity will be presented using CTCAE grade.

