6.2 Imputation Rules for Partial Dates

Imputed dates and time will NOT be presented in the listings.

Table 6 and Table 7 present algorithm for imputing partial dates for TEAE and prior/concomitant medication respectively.

Table 6	Algorithm f	r Treatment-Emergent Adverse Events:	

Start/Increase Severity Date	Stop Date	Action
Known	Known	Considered as a treatment-emergent adverse event (TEAE) if start date on or after the date of the first dose of investigational product (IP)
	Partial	Considered as a TEAE if start date on or after the date of the first dose of IP. The last day of the month and the last month (ie, December) will be used if the stop day/month is missing.
	Missing	Considered as a TEAE if start date on or after the date of the first dose of IP
Partial, but known components show that it cannot be on or after first IP taken date	Known	Not a TEAE. The first day of the month and January will be used if the start day/month is missing.
	Partial	Not a TEAE. The first day of the month and January will be used if the start day/month is missing. The last day of the month and the last month (ie, December) will be used if the stop day/month is missing.
	Missing	Not a TEAE. The first day of the month and January will be used if the start day/month is missing.
Partial, could be on or after first IP taken date	Known	Considered as TEAE, if stop date is after first IP taken date. The first IP taken date will be used if start date is in the same month/year with first IP taken date, or the first day of the month and January will be used if the start day/month is after first IP taken date Considered as not TEAE, if stop date is prior to first IP taken date. The first day of the month and January will be used if the start day/month is missing.
	Partial	Considered as TEAE. The first IP taken date will be used if start date is in the same month/year with first IP taken date, or the first day of the month and January will be used if the start day/month is after first IP taken date. The last day of the month and the last month (ie, December) will be used if the stop day/month is missing.
	Missing	Considered as TEAE. The first IP taken date will be used if start date is in the same month/year with first IP taken date, or the first day of the month and January will be used if the start day/month is after first IP taken date.
Missing	Known	Considered as TEAE if stop date is on or after the date of the first dose of IP.

Parexel International

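### SAP 4.13.1 and Table 6 give two unreconciled TEAE rules for onset on Day 1 before dosing, and one Table 6 cell leaves a stop date on the dosing day unclassified

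*SAP*

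**What the plan says.** The primary endpoint is "Incidence of TEAEs and TESAEs" (SAP 2.1).

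SAP 4.13.1 defines a TEAE by reference to the act of dosing: "an AE that started after study drug administration or pre-existed that worsened in severity after study drug administration".

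SAP 6.2, Table 6, gives an algorithm for the same classification. Although the section is headed as imputation for partial dates, the table's first three cells cover start (or severity-increase) dates that are fully known, with the stop date known, partial or missing. All three use the calendar date: "Considered as a TEAE if start date on or after the date of the first dose of IP". They have no time component and no exception for pre-dose events on Day 1.

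Further down, for a partial start that could fall on or after dosing with a known stop date, Table 6 has two branches: "Considered as TEAE, if stop date is after first IP taken date" and "Considered as not TEAE, if stop date is prior to first IP taken date". For a missing start with a known stop date it says: "Considered as TEAE if stop date is on or after the date of the first dose of IP".

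On data collection, Protocol 8.3.1 says "All AEs and SAEs will be collected from the signing of the ICF until the EOS visit on Day 75". Protocol 6.4 has the date and time of dosing recorded in the eCRF.

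**The concern.** Two rules in one SAP define the events that make up the primary endpoint, and they disagree for a defined set of events: those with onset, or worsening, on the dosing day but before the dose.

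Such events can occur. Participants are admitted on Day -1 and adverse events are collected from consent. Under the protocol's schedule of activities, Day 1 includes pre-dose vital signs, PK, PD and immunogenicity sampling, and triplicate ECGs "at 90, 75, and 60 minutes before dosing" (Protocol 8.2.3). A headache or a reaction at a venepuncture site in that window is not a TEAE under 4.13.1 but is one under Table 6. Two programmers following different sections would report different incidences from the same data.

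The stop-date gap is a separate and narrower matter. The relevant cell of Table 6 deals with stops before and after the dosing date but not on it, so the programmer has to decide.

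**Working it through.** **The plan's own figure.** The only design figure is the probability of at least one AE among 6 participants (SAP 3.2). The formula 1 − (1 − p)^6 gives 46.9% at p = 10%, 62.3% at 15%, 73.8% at 20%, 82.2% at 25%, 88.2% at 30%, 92.5% at 35% and 95.3% at 40%. All seven values reproduce. Nothing below depends on them.

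**Step 1: the two rules on the same events.** Assume a dose at 09:00 on Day 1; the clock time is illustrative.

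| Onset relative to dose | SAP 4.13.1 | Table 6, known start |
|---|---|---|
| 24 h before (Day -1) | not TEAE | not TEAE |
| 9.5 h before (Day -1) | not TEAE | not TEAE |
| 8.9 h before (Day 1) | not TEAE | TEAE |
| 1.5 h before (Day 1) | not TEAE | TEAE |
| 0.1 h before (Day 1) | not TEAE | TEAE |
| 0.1 h after | TEAE | TEAE |
| 4 h after | TEAE | TEAE |

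The rules differ only between midnight and dosing on Day 1. Comparing date-times would make every line agree.

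**Step 2: the stop-date cell.** With the start partial but possibly on or after dosing, and the stop known:

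| Stop date relative to dosing date | Partial-start cell | Missing-start cell |
|---|---|---|
| 1 day before | not TEAE | not TEAE |
| same day | unassigned | TEAE |
| 1 day after | TEAE | TEAE |

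**Step 3: size per affected participant.** Each cohort has 8 participants at 3:1, so 8 × 3/4 = 6 active and 8 × 1/4 = 2 placebo. Pooled placebo over six cohorts is 6 × 2 = 12. One participant is 1/6 = 16.7 points in an active cohort and 1/12 = 8.3 points in pooled placebo. Participants are counted once per category (Protocol 9.4.1), so the overall incidence moves by this much only if the participant has no other TEAE. For a single SOC or PT line, the condition is no other TEAE in that line.

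**Step 4: how often.** The documents give no rate for pre-dose Day 1 events. Taking an assumed rate q per participant, the chance of at least one such participant among 48 is 1 − (1 − q)^48 and the expected number is 48q:

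| Assumed q | P(at least 1 of 48) | Expected number |
|---|---|---|
| 0.5% | 21% | 0.24 |
| 1% | 38% | 0.48 |
| 2% | 62% | 0.96 |
| 5% | 91% | 2.4 |

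These are chances that an event arises on which the rules disagree. The chance that a reported participant-level incidence changes is lower, because of the condition in Step 3.

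**The case against.** The strongest answer is that 4.13.1 is the definition and Table 6 only handles incomplete dates. It sits in an appendix on partial dates and is introduced as imputation. On that reading pre-dose Day 1 events stay out of the endpoint. The reading is reasonable, but the SAP does not state it, and the table's known-start cells impute no start date: they classify. The protocol does not settle the matter either; it uses the term TEAE without defining it. What stands is that the consequence is conditional. A reader might infer that pre-dose events do enter the primary endpoint; the documents support this only if Table 6 is the rule applied.

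Second, the documents do not confirm that AE onset time is collected. The eCRF is cited in the SAP but is not part of the documents. Dosing time is recorded, and 6.2 mentions imputed times in passing, which is only a hint. If onset time is not collected, a date rule is the practical choice, and it should then be stated as a convention in 4.13.1.

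Third, the effect is limited. The date rule over-includes and does not hide events. It applies identically to active and placebo, and no hypothesis is tested. All adverse events, including pretreatment ones, are listed, so an affected case remains visible. This stands, and it keeps the point minor.

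Fourth, the stop-date gap needs a partial start and a stop exactly on the dosing day, in participants who are resident from Day -1. Where the start is partial or missing and dates leave doubt, the table elsewhere tends to default to TEAE, so the intention can be guessed. It is still not written.

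**Conclusion.** The point holds as an unreconciled definition of the primary endpoint plus one unassigned case. Both are in the current SAP text. If Table 6 is applied, onset or worsening on Day 1 before dosing counts as a TEAE although 4.13.1 excludes it; if 4.13.1 is applied, it does not count. The SAP does not choose.

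The size is 16.7 points in a 6-participant active cohort or 8.3 points in pooled placebo, for one affected participant with no other TEAE. The expected number of such participants is small: 0.24 to 2.4 among 48 under assumed rates of 0.5% to 5%, which are not in the documents. A reader might also infer a bias between active and placebo; the documents do not support that, since the same rule applies to both. This is a minor correction.

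**What to change.** In the three known-start cells of Table 6, where the time of AE onset or severity increase is recorded, classify the event as a TEAE only if that date-time is after the dosing date-time. This matches 4.13.1 and keeps its worsening limb. Where the Day 1 time is not recorded, count the event as a TEAE and say in the SAP that this is a convention.

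In the one cell for a partial start that could fall on or after dosing with a known stop, change after to on or after the dosing date, as in the missing-start row. Leave the stop-date handling of all other rows unchanged. A stop-date test applied to every row would turn events that began before dosing and merely continued past it into TEAEs, against 4.13.1.

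The cost is four cells of text, a check of whether the eCRF captures AE onset time, and a small change to the derivation program. SAP section 1 already provides a modification form for changes after finalization. No new data collection is needed, because the stated convention covers missing times.

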6.3 Laboratory Test Parameters

ALXN1910-HV-101

Statistical Analysis Plan

Category	Lab Parameter
Hematology	Red blood cell count
	Hematocrit
	Red blood cell indices:
	Mean corpuscular volume
	Mean corpuscular Hemoglobin
	Mean corpuscular hemoglobin concentration
	Reticulocytes
	Monocytes
	Eosinophils
	Basophils
	Platelet count
	Mean platelet volume
	White blood cell count
	Neutrophils
Clinical Chemistry	Blood urea nitrogen/urea
	Potassium
	Creatinine
	Sodium
	Chloride
	HbA1c
	Creatine kinase
	AST/SGOT
	ALT/SGPT
	Gamma-glutamyltransferase
	Alkaline phosphatase
	Total and direct bilirubin
	Indirect bilirubin
	Total protein
	Albumin
	Calcium including ionizedcalcium
	Phosphate
	Urea
	Magnesium
	Bicarbonate
	Prothrombin time
Coagulation	Partial thromboplastin time
5	International normalized ratio
Other safety laboratory	Antidrug antibodies (Alexion)
tests	The following tests are to be conducted in case of an acute injection/infusion-associated
	reaction:
	Tryptase (Alexion)
	C5b-9 (Alexion)
	Hematology, chemistry, and urinalysis panels
Routine urinalysis (by	Specific gravity, pH, glucose, protein, blood, ketones, bilirubin, urobilinogen, nitrite,
	erythrocytes, and leukocyte esterase

Statistical Analysis Plan

	Microscopic examination (if any leukocytes, trace protein, nitrites, and blood [if not
	menstruating] are abnormal)
Urine electrolyte	Urine for calcium, phosphorus, and creatinine
Other screening tests	Urine drug and alcohol tests
	FSH (confirmation of postmenopausal state)
	HIV-1 and HIV-2 antibodies, HbsAg, anti-HBC IgG + IgM (if IgG positive), and anti-HCV
	Serum human chorionic gonadotropin pregnancy test
	Serum or urine pregnancy tests

Abbreviations: ALT = alanine aminotransferase; anti-HBC = hepatitis B core antibody; anti-HCV = hepatitis C virus antibody; AST = aspartate aminotransferase; C5b-9 = terminal complement complex; FSH = follicle-stimulating hormone; HbsAg = hepatitis B surface antigen; HIV = human immunodeficiency virus; IgG = immunoglobulin G; IgM = immunoglobulin M; SGOT = serum glutamic-oxaloacetic transaminase; SGPT = serum glutamic-pyruvic transaminase

6.4 ECG Notable Criteria

ECG Parameters	Definition/threshold	
QT, QTcF	QTcF interval \leq 450 msec	
	$450 \text{ msec} \le \text{QT}, \text{QTcF interval} \le 480 \text{ msec}$	
	$480 \operatorname{msec} < QT, QTcF \operatorname{interval} \le 500 \operatorname{msec}$	
	QT, QTcF interval > 500 msec	
	QT, QTcF interval increases from baseline ≤ 30 msec	
	30 msec $<$ QT, QTcF interval increases from baseline \le 60 msec	
	QT, QTcF interval increases from baseline > 60 msec	

ECG = electrocardiogram; bpm = beats per minute; QTcF = QT corrected using Fridericia's formula

6.5 Sample SAS Code for statistical analysis

Dose proportionality analysis

ODS OUTPUT parameterestimates=est FitStatistics=fit;

PROC REG DATA = PP ALPHA=0.05 PLOTS=ALL;

BY PARAMCD PARAM;

MODEL LNAVAL=LNDOS/CLB;

RUN;

where:

LNAVAL: natural log-transformed PK parameter

LNDOS: natural log-transformed dose level of ALXN1910

PARAM: PK parameter

SUBJECT: participant

ALXN1910-HV-101

Statistical Analysis Plan

Absolute Bioavailability analysis

ODS SELECT NOPRINT(NOWARN);

ODS OUTPUT CovParms= Cv1 lsmeans=lsm estimates=est Diffs=diff1;

PROC MIXED DATA=DATA1 NOITPRINT;

BY COMPOUND PPSPEC PARAMN PARAMCD PARAM;

CLASS SUBJID TRTA;

MODEL LN_PK = TRTA/DDFM=KR;

RANDOM SUBJID;

LSMEANS TRTA/PDIFF ALPHA=0.05 CL;

ESTIMATE "SC vs IV" TRTA 1 -1 /CL ALPHA=0.05;

RUN;

where:

COMPOUND: compound used in the study

PPSPEC : Specification (Serum)

PARAMN : numerical order of PK parameter

PARAMCD :short name of PK parameter

PARAM: PK parameter

LN_PK; natural log transformed value of PK parameter

SUBJID: Participant

TRTA: actual treatment

Ethnicity Comparison

Sample SAS Code:

ODS SELECT NOPRINT(NOWARN);
ODS OUTPUT CovParms= Cv1 lsmeans=lsm estimates=est Diffs=diff1;
PROC MIXED DATA=DATA1 NOITPRINT;
BY COMPOUND ANALYTE PPSPEC PARAMN PARAMCD PARAM;
CLASS SUBJID ETHNICITY;
MODEL LN_PK = ETHNICITY/DDFM=KR;
RANDOM INT SUBJID ;
LSMEANS ETHNICITY/PDIFF ALPHA=0.05 CL;
ESTIMATE "JAPANESE vs NON-JAPANESE" ETHNICITY 1 -1 /CL ALPHA=0.05;

RUN;

where:

Statistical Analysis Plan

COMPOUND: compound used in the study

ANALYTE : analyte of the drug (can be parent or metabolite)

PPSPEC : Specification (serum)

PARAMN : numerical order of PK parameter

PARAMCD :short name of PK parameter

PARAM: PK parameter

LN_PK; natural log transformed value of PK parameter

SUBJID: Participant

Approval Signatures

Document Name:	Statistical Analysis Plan 28 Mar 2023 ALXN1910-HV-101
Document Number:	VV-TMF-3755505
Parexel Version Number:	
System Version Number:	1.0

Document Approvals	PPD
Reason for signing: Approved	
Reason for signing: Approved
